### 8.2.2. PK Parameters

Pharmacokinetic parameters will be generated for all subjects for whom parameters can be derived. The analyte and parameters will be used to evaluate the PK objectives of the study. The primary PK parameters are  $AUC_{last}$ ,  $AUC_{inf}$ , and  $C_{max}$  of VES.

**Table 8-1. PK Parameters for VES**

Analyte	Parameters
VES (Single Dose)	$C_{max}$ , $T_{max}$ , $C_{last}$ , $T_{last}$ , $AUC_{last}$ , $AUC_{inf}$ , $\%AUC_{exp}$ , $T_{1/2}$ , $Vz/F$ , $CL/F$ , and $\lambda_z$

### 8.3. Statistical Analysis Methods

#### 8.3.1. General Considerations for Statistical Analyses

Individual subject concentration data and individual subject PK parameters of VES will be listed and summarized for subjects in the VES PK analysis set by treatment. Summary statistics (n, mean, SD, coefficient of variation [CV(%)], minimum, median, maximum, Q1, Q3) will be presented by treatment group. The number of subjects with concentration values BLQ will be presented. The geometric mean, geometric mean 95% CI, and the mean and SD of the natural log-transformed values will be presented for all PK parameters in addition to the summaries mentioned above.

Plasma concentrations over time will be plotted in the semi-logarithmic and linear scale as mean  $\pm$  SD, and median (Q1, Q3) by treatment. In addition, individual subject plasma concentrations over time will be plotted by treatment group.

#### 8.3.2. Dose Proportionality

If data are available, dose proportionality will be obtained by comparing PK parameters of VES across all dose levels for Cohorts 1-6.

Dose proportionality will be evaluated based on the power model and the ANOVA method.

The following PK parameters and dose levels will be included in both the power model and ANOVA method:

	Day	Doses (mg)	PK Parameters
VES (single dose)	1	1, 2, 4, 6, 8, 10, 12	$AUC_{last}$ , $AUC_{inf}$ , $C_{max}$

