1.2.3.1. GS-US-243-0101

Study GS-US-243-0101 was a first-in-human, randomized, double-blind, placebo-controlled, single ascending dose (SAD) study of GS-9620 in 75 healthy male and female subjects. The primary objective of the study was to evaluate the safety and tolerability of GS-9620 and the secondary objectives were to characterize the plasma PK/PD profile of GS-9620. Doses used were: 0.3, 1, 2, 4, 6, 8, and 12 mg.

The treatment was generally well tolerated. There were no Grade 4 AEs or serious adverse events (SAEs) reported, and most AEs were mild. No individual subject discontinued due to AEs or laboratory abnormalities. Treatment-emergent Grade 3 AEs included pyrexia in 2 subjects who received GS-9620 12 mg. A higher incidence of flu-like symptoms was also reported in subjects administered the higher doses (8 and 12 mg). Myalgia and headache were reported by subjects in both the 8 and 12 mg cohorts, while pyrexia and chills were only reported by subjects in the 12 mg cohort.

Plasma concentrations of GS-9620 peaked between 1.5 and 6 hours after dosing and declined gradually over 48 hours. The mean maximum plasma concentration (C_{max}) ranged from 184.2 pg/mL at the 0.3 mg dose to 11.97 ng/mL at the 12 mg dose. Exposures were higher in the fasted state than in the fed state. After the 1 mg, 2 mg, and 4 mg doses, GS-9620 was detectable at 48 hours after dosing and had a median terminal half-life between 17.16 and 26.96 hours.

Three ISGs were analyzed: ISG15, MX-1 and OAS-1. Significant ISG induction was observed at the 2-mg dose and above. ISG15 mRNA expression showed the highest induction compared to MX-1 and OAS-1. Serum IFN- α was detected transiently in subjects who received the 8 or 12 mg doses, and only the 12 mg cohort had a >2-fold mean change in serum IFN- α from baseline. A dose-dependent induction was observed for serum IP-10 but not for IFN- α or TNF- α . Dose-dependent T cell activation was also observed at the 2 mg dose and above.

In summary, single doses of GS-9620 up to 12 mg were well tolerated, with significant ISG induction and T cell activation at doses of 2, 4, and 6 mg in the absence of detectable serum IFN- α or systemic AEs.

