1.4. Rationale for Dose Selection/Dosing Interval

In 50 HCV and in 100 HBV patients, doses of up to 4 mg of GS-9620 were evaluated, either as a single dose or two doses one week apart. Safety data from these studies demonstrated that GS-9620 is well-tolerated with no evidence of dose dependent adverse events or laboratory abnormalities that are consistent with systemic immune activation such as flu-like symptoms, hematologic reductions or increases in liver enzymes including transaminases. In the majority of patients there was no detectable IFN- α in serum, consistent with the mechanism of action of pre-systemic innate immune system activation in the GALT and/or in the liver. Evidence of biological activity was observed in a dose dependent manner in these studies, with maximal induction of ISG15 occurring within 48 hours and return to baseline levels of expression within 168 hours (7 days). In addition, the safety of a weekly dosing interval was supported by the observed elimination half-life (median range ~ 8 to 25 hours for 1, 2, or 4 mg doses in HBV- or HCV-infected subjects) and that no accumulation of GS-9620 occurred following once-weekly dosing.

A dosing schedule of once every 2 weeks is planned for this protocol in order to verify the resolution of GS-9620-induced HIV-1 viremia prior to additional dosing. This schedule is more conservative than the weekly administrations used in the Phase 1 evaluations across the above-referenced studies in chronic hepatitis B and C patients.

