The highest GS-9620 dose planned to be assessed in this clinical study may be up to 12 mg. Dose selection has been based on the results from the study in healthy volunteers (GS-US-243-0101) that showed dose-dependent ISG mRNA induction from 0.3 mg up to 12 mg in the absence of dose-dependent induction in serum IFN- α . As described above, dose escalation to Cohort 6 (GS-9620 10 mg) for the proposed study is also based on interim safety data from the ongoing 8 mg cohort (Cohort 5) as described above. CCI

With regard to the proposed adaptive cohorts, food affects absorption of GS-9620 and administration of GS-9620 4 hours post-ingestion of a high fat meal in Study GS-US-243-0101 resulted in approximately 30% reduction of systemic exposures of GS-9620, minimal effect on PD biomarkers and improved tolerability. Dosing GS-9620 with an acidic solution may improve the solubility and absorption of the compound. CCI

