5.3.1. Fasting and food/liquids Requirement

The following fasting guidelines should be followed by subjects on all dosing days

Table 5-1. Fasting and food/liquids Requirement

Cohort	Fasting Period	Water/liquids Permitted	Water/liquids at Dosing
1 to 4	At least 2 hours prior to and after dosing ^a	1 hour prior to and 2 hours after dosing	240 mL of water
5, 6, CCI	Overnight ^b (at least 8hrs before dosing for Cohorts 5, 6 CCI and at least 2 hours after dosing)	1 hour prior to and 2 hours after dosing	240 mL of water

CCI

- a If subjects eat prior to the 2 hour fasting period before study drug dosing, no more than a light meal should be eaten (as described in the PK Sample Collection, Processing, Storage, and Shipment Manual).
- b If subjects did not fast overnight, plasma GS-9620 Intensive PK must not be completed. The subject should be counseled regarding proper fasting requirement and asked to return for the Intensive PK collection.

For Cohorts 1 to 4, GS-9620 or placebo should be taken by subjects with approximately 240 mL of water on an empty stomach. Food will not be permitted between at least 2 hours prior to and until 2 hours after dosing. Aside from the 240 mL of water provided at dosing, water/liquids will not be permitted from 1 hour prior to until 2 hours after dosing. If subjects eat prior to the 2 hour fasting period before study drug dosing, no more than a light meal should be eaten (as described in the PK Sample Collection, Processing, Storage, and Shipment Manual).

For Cohorts 5, 6 CCI, GS-9620 or placebo should be administered with 240 mL of water after an overnight fast (nothing but water for ≥ 8 hours prior to dosing).

CCI

[Note: For all cohorts, other than the water or cranberry juice provided with dosing, water and other fluids will be prohibited for 1 hour before and 2 hours after dosing.]

CCI

CCI

CCI

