to 6, CCI of their assigned study treatment administered once every other week. For all subjects in Cohort 6, Dose 4 (Day 43) will occur after SEC review has been completed. If dose escalation is approved by the SEC, subjects in Cohort 6 will receive 12 mg of VES or placebo from Doses 4 to 10; if dose escalation is not approved by the SEC, subjects will continue receiving 10 mg of VES or placebo from Doses 4 to 10.

For Cohorts 1 to 3, dosing visits will occur at Day 1, Day 15, Day 29, Day 43, Day 57, and Day 71. For Cohorts 4 to 9, dosing visits will occur at Day 1, Day 15, Day 29, Day 43, Day 57, Day 71, Day 85, Day 99, Day 113 and Day 127. CCI

For Cohorts 1 to 4, subjects will fast for at least 2 hours before dosing. For Cohorts 5 to 8, subjects will fast overnight (at least 8 hours) before dosing. CCI

The Investigator will verify the subject's continued eligibility for dosing at post-Baseline dosing visits, including the absence of DLTs and (for females of childbearing potential) a negative urine pregnancy test, prior to dosing. All doses will be directly administered by blinded site staff.

Laboratory analyses (hematology, serum chemistry, and urinalysis) will be performed weekly for Cohorts 1 to 3. For Cohorts 4 to 9, these labs will be collected on dosing days, seven days post dose (starting from Dose 4), at end of study, and early study drug discontinuation (ESDD). For Cohorts 6, CCI these labs will also be collected on Day 2 and two days post dose (starting from Dose 5). CCI

Urine pregnancy test (for females of childbearing potential) will be performed prior to each dose. Vital signs (blood pressure, pulse, respiration rate and temperature) will be measured at all dosing visits.

Plasma HIV-1 RNA will be measured at every visit except Pre-Baseline (Day -13). Cell-associated HIV-1 RNA/DNA (CAVR/CAVD), and plasma HIV-1 RNA by SCA will be collected immediately before and two days post Doses 1, 4, 6 and at end of the study (Cohort 1 to 3); immediately before and two days post Doses 1, 5, 10 and at end of the study (Cohorts 4 to 9). CCI

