### **3.3. Strata and Covariates**

This study does not use a stratified randomization schedule in enrolling subjects. No covariates will be included in analyses.

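### SAP 3.1.4 requires a steady-state PK parameter that is not planned, and SAP 8.3.2 lists 12 mg as a Day 1 dose and ignores repeat profiles; the fasting change between 6 and 8 mg needs a label (minor)

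*SAP*

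**What the plan says.** **PK set.** SAP 3.1.4 admits subjects who were randomized, took at least one active dose and have at least one nonmissing steady-state parameter. SAP 8.2 and 8.3.1 use that set for PK parameters and summaries. Table 8-1 and the Appendix 1 list of parameters to be calculated hold single-dose parameters only. Protocol 8.2.1.4.1 asks only that PK parameters be available, and SAP 8.2.2 generates them for every subject in whom they can be derived.

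**Dose proportionality.** Under SAP 8.3.2, "dose proportionality will be obtained by comparing PK parameters of VES across all dose levels for Cohorts 1-6", by a power model and an ANOVA, each with dose as its only term. SAP 3.3 adds: "No covariates will be included in analyses". The table has one row, Day 1, with doses 1, 2, 4, 6, 8, 10 and 12 mg, and the ANOVA contrasts carry seven coefficients. The power-model code has `class subjid` but no RANDOM or REPEATED statement. No acceptance boundaries are set.

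**Cohort 6.** SAP 1.2 gives 10 mg for Doses 1 to 3, then 12 mg from Dose 4 (Day 43) if the safety committee approves. SAP 8.1 plans a full PK profile on Day 43.

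**Fasting.** SAP 1.2: "For Cohorts 1 to 4, subjects will fast for at least 2 hours before dosing. For Cohorts 5 to 8, subjects will fast overnight". Protocol 5.3.1 adds for Cohorts 1 to 4: "If subjects eat prior to the 2 hour fasting period before study drug dosing, no more than a light meal should be eaten". On an earlier healthy-volunteer study, protocol 1.2.3.1 reports: "Exposures were higher in the fasted state than in the fed state".

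**The concern.** The PK set is defined on something the SAP does not plan to calculate, and it governs every PK result; PK is a secondary objective.

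The dose-proportionality table describes a Day 1 data set that cannot exist. If the Day 43 profile is added to supply 12 mg, six subjects appear twice in a regression that takes all profiles as independent, so the slope's interval is too narrow.

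Fasting regimen also switches at a single point on the dose scale. A reader of the slope, or of an 8 to 1 mg ratio, would not learn from SAP 8.3.2 that a departure from proportionality could come from fasting as well as from dose.

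**Working it through.** **A. PK set.** Steady-state parameters in Table 8-1: none. In the Appendix 1 calculation list: none (no AUCtau or Ctau). Appendix 1 does define a steady-state CL/F, and Appendix 3 gives decimal places for AUCtau, CLss/F and Ctau, but neither adds them to what is calculated. Read literally, no subject qualifies, or at most the six active Cohort 6 subjects if Day 43 is called steady state.

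**B. Dose levels.** The plan's figure is seven levels on Day 1. The cohort definitions give six (1, 2, 4, 6, 8, 10 mg), with 6 × 6 = 36 active subjects. The seventh can come only from Day 43, giving 42 profiles from 36 subjects. Seven-coefficient contrasts do not match a six-level factor; the code was not run in SAS.

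Can Day 43 count as a single dose? Protocol 1.2.3.1 gives, for 1 to 4 mg, a "median terminal half-life between 17.16 and 26.96 hours". The dosing interval is 14 × 24 = 336 h; 336 / 26.96 = 12.5 half-lives, and 2^-12.5 is about 0.0002, so about 0.02% remains. Protocol 1.4 also reports that "no accumulation of GS-9620 occurred following once-weekly dosing". A single-dose reading is reasonable.

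**C. Ignoring the pairing.** Assumptions: log-normal exposure, CV 60%, six subjects per level, true slope 1, no fasting effect, within-subject correlation ρ.

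- sd = √ln(1 + 0.6²) = 0.5545
- Sum of squares of ln dose over 42 profiles = 29.65, so the nominal slope SE = 0.5545 / √29.65 = 0.102 and the 90% half-width = 1.684 × 0.102 = 0.171
- Mean ln dose is 1.534; centred values are 0.769 at 10 mg and 0.951 at 12 mg
- True variance / nominal variance = 1 + 2ρ × 6 × 0.769 × 0.951 / 29.65 = 1 + 0.296ρ

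| ρ | True SE / nominal SE | Slope 90% CI misses (40,000 simulated trials) |
|---|---|---|
| 0.3 | 1.04 | 11.4% |
| 0.5 | 1.07 | 12.4% |
| 0.8 | 1.11 | 14.0% |

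With a random subject effect (10,000 trials), misses are 9.7% and 10.7% at ρ 0.5 and 0.8. The 12 to 1 mg ANOVA contrast uses one profile per subject at each dose and is not distorted (10.4% and 10.0%).

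**D. Fasting.** No dose in Cohorts 1 to 6 is given under both regimens. Adding an overnight-fast indicator to the ANOVA leaves the rank at 6 (six levels) or 7 (seven levels), so ratios of 8, 10 and 12 mg to 1 mg are fully aliased with fasting. Ratios of 2, 4 and 6 mg to 1 mg, and comparisons among 8, 10 and 12 mg, lie within one regimen.

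In the power model, the indicator correlates with ln dose at 0.72 (six levels) or 0.78 (seven). Its regression coefficient on ln dose is b = 0.420 or 0.458. If exposure under the shorter fast is lower by a fraction q, the slope shifts by b × ln(1/(1 − q)) and the ratios are multiplied by 1/(1 − q). For q = 0.20 and six levels, the shift is 0.420 × 0.223 = 0.094.

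| Assumed q | Ratio of 8 mg or more to 1 mg, multiplied by | Slope, true 1.00, six levels | Seven levels |
|---|---|---|---|
| 0 | 1.00 | 1.00 | 1.00 |
| 10% | 1.11 | 1.04 | 1.05 |
| 20% | 1.25 | 1.09 | 1.10 |
| 30% | 1.43 | 1.15 | 1.16 |

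**The case against.** The strongest reply is that little hangs on this. Protocol 8.7 does not plan dose proportionality. The SAP calls it exploratory, sets no boundaries, and uses it for no decision. The 12 mg row is a day-label slip that SAP 1.2 and 8.1 let a careful programmer correct, and a programmer would probably follow SAP 8.2.2 on who contributes parameters. The fasting change is a design limit already visible in SAP 1.2, which no analysis of these data can remove. All of that stands, and it keeps the point minor. It does not make the PK-set definition, the Day 1 row or the unused subject term right as written.

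A reader might infer three stronger things that the documents do not support:

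- **The whole dose comparison is confounded with fasting and biased by about 30%.** Full aliasing holds only for ratios of 8 mg or more to 1 mg. The 30% figure (protocol 1.4: "resulted in approximately 30% reduction of systemic exposures of GS-9620") is for dosing 4 h after a high-fat meal. Cohorts 1 to 4 fast at least 2 h, and the light meal is a ceiling for those who eat. No figure for a 2 h against an overnight fast is given; it may be near zero.
- **There are no 12 mg data.** The Day 43 profile is planned.
- **The PK tables will be empty.** That follows only from the literal wording of SAP 3.1.4, against SAP 8.2.2 and the protocol's own set.

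**Conclusion.** Two SAP rules are wrong as written. The PK set requires a steady-state parameter when none is planned. The Day 1 row includes a dose first possible on Day 43, in the subjects who took 10 mg on Day 1, and the power-model code ignores the pairing. The second fault raises the slope CI's miss rate from 10% to about 11 to 14%; CV 60% and correlation 0.3 to 0.8 are assumptions, as the documents give neither.

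The fasting point is a limit to disclose. Its size is unknown; the 0 to 30% range above only illustrates it, and at 10% the slope moves by 0.04 to 0.05.

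Severity is minor. The dose-proportionality faults touch PK conclusions only, and the PK-set fault is a wording conflict.

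**What to change.** 1. **SAP 3.1.4:** replace *steady state PK parameter* with *PK parameter*, in line with the protocol. Cost: two words.
2. **SAP 8.3.2 table and code:** list Day 1 doses as 1, 2, 4, 6, 8 and 10 mg, and 12 mg as Cohort 6 Day 43. Match the ESTIMATE statements to the levels present, and add a random subject effect when Day 43 is included. Cost: a pooled slope CI 6 to 8% wider (half-width 0.182 to 0.186 against 0.171 at CV 60%).
3. **Fasting:** keep both planned models. Label the overall slope and the ratios of 8, 10 and 12 mg to 1 mg as confounded with fasting regimen. Add the 1 to 6 mg slope and the ratios of 10 and 12 mg to 8 mg. These are less precise. At assumed CV 40/60/80% the 1 to 6 mg slope has a 90% half-width of 0.20/0.28/0.36, against 0.13/0.19/0.25 for the six-level slope, and the 10 to 8 mg ratio is known to within a factor of 1.46/1.72/1.99.

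A fasting-adjusted slope is not worth adding. With six levels, 8 and 10 mg supply 0.149 / 11.35 = 1.3% of its information, so it nearly repeats the 1 to 6 mg slope, and it would credit any true step at 8 mg to fasting.

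No new data are needed. Item 3 discloses the fasting limit; it cannot remove it.

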### Power Model

The dose proportionality analysis will be addressed in terms of point estimates and CIs of statistical model parameters (slopes). The power model has the general equation  $y = \beta_0 \times \text{dose}^{\beta_1}$  where  $y$  represents the dependent variables, eg,  $AUC_{\text{last}}$ ,  $AUC_{\text{inf}}$ , and  $C_{\text{max}}$  for VES single-dose. The exponent  $\beta_1$  in the model will be assessed by regressing the natural log-transformed PK parameter on the natural log-transformed dose {[Smith 2000](#)},

$$\log(y) = \log(\beta_0) + \beta_1 \log(\text{dose})$$

The population mean slope  $\beta_1$  and corresponding 90% confidence interval (CI) will be estimated.

The following SAS® PROC MIXED code will provide the analysis and the 90% CI calculations for natural log-transformed  $C_{\text{max}}$ . Similar code will be used for other natural log-transformed parameters.

```
proc mixed;  
  class subjid;  
  model lncmax = lndose / ddfm=kr;  
  estimate "Slope of log dose" lndose 1/ cl alpha=0.10;  
  make 'estimates' out=slope1;  
run;
```

Due to the exploratory nature of the analysis, no dose proportionality boundaries are explicitly stated.

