## 1.2. Study Design

This is a phase 1b, randomized, double-blinded, placebo-controlled, multi-cohort dose-escalation study with dose cohorts: Cohort 1 (1 mg Dose), Cohort 2 (2 mg Dose), Cohort 3 (4 mg Dose), Cohort 4 (6 mg Dose), Cohort 5 (8 mg Dose), Cohort 6 (three administrations of 10 mg Dose, followed by seven administrations of 12 mg Dose; Safety Evaluation Committee [SEC] review of the 10mg safety data will be required prior to dose escalating to 12mg), and optional Cohort 7

CCI

Two additional optional adaptive cohorts, Cohort 8

CCI

and Cohort 9

CCI

HIV-1 infected male and non-pregnant, non-lactating female adults who have been virologically suppressed (HIV-1 RNA < 50 copies/mL) on ART for  $\geq 12$  consecutive months prior to screening may be eligible for entry (refer to the protocol for complete inclusion and exclusion criteria). Eligible subjects are randomly assigned to 1 of the following 2 treatment groups in a 6:2 ratio for each cohort. CCI

- Cohort 1 (n = 8): Blinded VES 1 mg (n = 6) vs. Placebo (n = 2)
- Cohort 2 (n = 8): Blinded VES 2 mg (n = 6) vs. Placebo (n = 2)
- Cohort 3 (n = 8): Blinded VES 4 mg (n = 6) vs. Placebo (n = 2)
- Cohort 4 (n = 8): Blinded VES 6 mg (n = 6) vs. Placebo (n = 2)
- Cohort 5 (n = 8): Blinded VES 8 mg (n = 6) vs. Placebo (n = 2)
- Cohort 6 (n = 8): Blinded VES 10/12 mg (n = 6) vs. Placebo (n = 2)

Central randomization is used. Enrollment will initially be opened for Cohort 1 only. The SEC will review study progress, safety and virology results of enrolled subjects. After all subjects in a cohort have received at least three doses (Cohorts 1 to 3, and 6) or five doses (Cohorts 4 and 5), the SEC will review safety data from that cohort, including adverse events (AEs) and clinical laboratory results (including plasma HIV-1 RNA) before approving the next dose escalation. CCI

A cohort may be suspended if  $\geq 2$  out of 6 subjects receiving VES experience one or more dose-limiting toxicities (DLTs) considered related to study drug. Subjects will receive a total of either 6 doses in Cohorts 1 to 3, 10 doses in Cohorts 4

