## 8. PHARMACOKINETIC ANALYSES

### 8.1. PK Sample Collection

Plasma VES (concentrations will be collected at the following time points **for all cohorts** relative to the Dose 1 on Day 1:

- Pre-dose ( $\leq 5$  minutes prior to dosing), 0.5, 1, 2, 4, 6, 8, 10, and 12 hours post-dose at Day 1; then one sample 48 hours post dose at Day 3

Plasma VES concentrations will be collected at the following time points **for Cohort 6** relative to the Dose 4 on Day 43:

- Pre-dose ( $\leq 5$  minutes prior to dosing), 0.5, 1, 2, 4, 6, 8, 10, and 12 hours post dose at Day 43; then one sample 48 hours post-dose at Day 45.

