### Analysis of Variance (ANOVA)

An ANOVA model using PROC MIXED will be used to estimate the ratio of the PK parameter at each dose level to the PK parameter at the reference dose. The parameters will be dose-normalized and natural log-transformed prior to analysis. The reference dose is 1 mg, determined by the PK scientist. Dose normalization is calculated by dividing each PK parameter value by the test dose/reference dose ratio. The ratio of geometric least-squares means (GLSM) and the corresponding 90% CI will be estimated for each PK parameter of interest.

The statistical model will include dose as a fixed effect {[U.S. Department of Health and Human Services Food and Drug Administration Center for Drug Evaluation and Research \(CDER\) 2003](#)}, {[U.S. Department of Health and Human Services Food and Drug Administration Center for Drug Evaluation and Research \(CDER\) 2001](#)}. The following SAS PROC MIXED code will provide the single dose comparison analysis and the 90% CI calculations for the natural log-transformed normalized PK parameter  $C_{\text{max}}$ . Similar code will be used for other natural log-transformed dose normalized PK parameters. The estimate statements assume that the treatment is ordered as VES 1 mg, VES 2 mg, VES 4 mg, VES 6 mg, VES 8 mg, VES 10 mg and VES 12 mg.

```
proc mixed;  
  class dose;  
  model lncmax = dose / ddfm=kr;  
  lsmeans dose/cl alpha=0.1;  
  estimate "VES 2 mg vs. 1 mg" dose -1 1 0 0 0 0 0 / cl alpha=0.10;  
  estimate "VES 4 mg vs. 1 mg" dose -1 0 1 0 0 0 0 / cl alpha=0.10;  
  estimate "VES 6 mg vs. 1 mg" dose -1 0 0 1 0 0 0 / cl alpha=0.10;  
  estimate "VES 8 mg vs. 1 mg" dose -1 0 0 0 1 0 0 / cl alpha=0.10;  
  estimate "VES 10 mg vs. 1 mg" dose -1 0 0 0 0 1 0 / cl alpha=0.10;  
  estimate "VES 12 mg vs. 1 mg" dose -1 0 0 0 0 0 1 / cl alpha=0.10;  
run;
```

The ESTIMATE statement is used to produce the point estimate and the corresponding 90% CI of the difference in PK parameters of interest on a logarithmic scale. The test-to-reference ratio and the 90% CI will be calculated by taking the exponential of the point estimate and the corresponding lower and upper limits.

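### The power-model code for dose proportionality has no subject effect, so if Cohort 6 supplies both the 10 mg and the 12 mg profiles the 90% CI for the slope is modestly too narrow

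*SAP*

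**What the plan says.** SAP 8.3.2 plans to assess dose proportionality by "comparing PK parameters of VES across all dose levels for Cohorts 1-6", using a power model and an ANOVA. Its table gives both methods the doses 1, 2, 4, 6, 8, 10 and 12 mg, all labelled single dose, Day 1.

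- **Power model.** The code is "model lncmax = lndose / ddfm=kr", with `subjid` in the CLASS statement and nowhere else. The slope and its "corresponding 90% confidence interval (CI) will be estimated".
- **ANOVA.** The code is "model lncmax = dose / ddfm=kr", with no mention of subject. Six ESTIMATE statements compare each higher dose, including 10 mg and 12 mg separately, with 1 mg.
- **Source of the top two doses.** SAP 1.2 lists "Cohort 6 (n = 8): Blinded VES 10/12 mg (n = 6) vs. Placebo (n = 2" and states that, if the SEC approves, "subjects in Cohort 6 will receive 12 mg of VES or placebo from Doses 4 to 10". SAP 8.1 places intensive sampling at Dose 1 in every cohort and, for Cohort 6, a second series "relative to the Dose 4 on Day 43".

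**The concern.** There are seven dose levels but only six active groups. No subject in Cohorts 1-6 receives 12 mg on Day 1, so the 12 mg level and its ESTIMATE statement need the Day 43 profiles. Those come from the same people who supply the 10 mg profiles. Two profiles of one drug in one person would be expected to correlate positively, yet the power-model code treats all profiles as independent. `ddfm=kr` makes no correction when the model has no random or repeated effect.

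What is at stake is the stated precision of the slope. The SAP sets no proportionality boundaries and reports this analysis through point estimates and intervals, so the interval is what readers will use.

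**Working it through.** The documents give no slope, SE or CI width to reproduce. The check rebuilds the design and compares the SE that the code would report with the true SE of the same estimate.

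**Inputs**
- Six active subjects per cohort (SAP 1.2; for example "Cohort 1 (n = 8): Blinded VES 1 mg (n = 6) vs. Placebo (n = 2").
- Doses 1, 2, 4, 6, 8, 10 and 12 mg (SAP 8.3.2), with 10 and 12 mg from the same six subjects. Profiles: 7 × 6 = 42. Subjects: 6 × 6 = 36.
- Two-sided 90% CI (`alpha=0.10` in the code).
- Assumed: equal variance σ² at each dose, and within-subject correlation ρ between the two Cohort 6 profiles, ranged from 0 to 0.9.

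**Position of the two doses.** Mean ln(dose) over the 42 profiles is 1.534 and Sxx = 29.65. The centred values are x10 = ln 10 − 1.534 = +0.769 and x12 = ln 12 − 1.534 = +0.951. They have the same sign, so positive ρ raises the slope variance.

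**True variance of the fitted slope**

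Var = (σ²/Sxx) × [1 + 2ρ·6·x10·x12/Sxx] = (σ²/Sxx) × [1 + 0.296ρ], because 12 × 0.769 × 0.951 / 29.65 = 0.296.

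**Variance the code reports, on average**

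The residual mean square has 42 − 2 = 40 df and expectation σ²(1 − 12ρh/40), where h = 1/42 + x10·x12/Sxx = 0.0238 + 0.0247 = 0.0485. The reported variance is therefore (σ²/Sxx) × [1 − 0.0145ρ].

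The SE ratio is the square root of the true bracket divided by the reported bracket. Coverage is from 200,000 simulations per ρ (not run at 0.1).

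| ρ | True bracket | Reported bracket | True SE / reported SE | Coverage of nominal 90% CI |
|---|---|---|---|---|
| 0 | 1.000 | 1.000 | 1.000 | 89.9% |
| 0.1 | 1.030 | 0.999 | 1.015 | – |
| 0.3 | 1.089 | 0.996 | 1.046 | 88.4% |
| 0.5 | 1.148 | 0.993 | 1.075 | 87.4% |
| 0.7 | 1.207 | 0.990 | 1.104 | 86.4% |
| 0.9 | 1.266 | 0.987 | 1.133 | 85.3% |

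**ANOVA.** Each contrast with 1 mg compares two separate groups of six subjects. Simulated coverage of the 10 vs 1 mg and 12 vs 1 mg intervals stays at 89.8-90.0% for ρ from 0.3 to 0.9.

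**Effect of a subject random intercept.** Fitted by REML with 34 df assumed (2,000 simulations per ρ), the mean CI half-width rises by 4.8%, 6.2%, 7.7% and 7.5% at ρ = 0.3, 0.5, 0.7 and 0.9. Coverage returns to about 90%; the Monte Carlo error is √(0.9 × 0.1/2000) ≈ 0.7 percentage points. For scale, with an assumed log-scale SD of 0.5 and ρ = 0.5, the half-width is about 0.154 as coded and 0.164 with the correlation modelled.

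**The case against.** **The table says Day 1.** Read literally, the model has 36 independent profiles, no 12 mg level and a valid interval, with slope SE 1/√23.32 = 0.207σ. Escalation depended on SEC approval, and SAP 8.3.2 applies only if data are available. This stands as a condition. But the literal reading contradicts the 12 mg entry in the same table row and the 12 mg ESTIMATE statement, and SAP 8.1 lists Day 43 sampling in Cohort 6 without qualification. The inclusive reading is the better one.

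**The analysis is exploratory and the effect small.** This stands. The correlation is assumed, and at 0.1 the SE is off by only 1.5%. PK is a secondary objective and no pass/fail rule uses the interval.

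**Stronger readings that a reader might infer.**
- *The slope is the only dose-proportionality inference.* It is not: SAP 8.3.2 also plans six ANOVA ratios with 90% CIs.
- *The top two doses dominate the slope.* They do not. Leverage per profile is 1/42 + x²/Sxx: 0.044 at 10 mg and 0.054 at 12 mg, against a mean of 2/42 = 0.048 and 0.103 at 1 mg. The slope variance is inflated because the two doses lie on the same side of the mean, not because their leverage is unusual.
- *The ANOVA ratios are invalid too.* They are not, as the coverage shows. All six share the 1 mg reference, so none was independent of the others in any case, and no 12 vs 10 mg contrast is planned.

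**Conclusion.** The concern holds, conditionally and at modest size. If the Day 43 profiles from Cohort 6 enter the power model, the code counts six subjects twice as though they were twelve. The true slope SE is then 1.02 to 1.13 times the reported one for ρ from 0.1 to 0.9, and coverage is about 85-88% for ρ from 0.3 to 0.9.

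This rests on a positive within-subject correlation that the documents do not give, on equal variance across doses, and on six evaluable profiles at each dose. The slope estimate itself is unbiased. It would be tempting to conclude that the dose-proportionality conclusion could be wrong. The documents do not support that, because they set no boundary for the interval to cross. What remains is overstated precision in one of two exploratory methods, together with a table label that cannot be right for the 12 mg level.

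**What to change.** 1. In the power model, add `random intercept / subject=subjid;` or `repeated / subject=subjid type=cs;`. Keep `ddfm=kr`, which then has a covariance structure to work on.
2. In the SAP 8.3.2 table, show the 12 mg level as Day 43 (Dose 4), Cohort 6, and keep Day 1 for the other doses.
3. Optionally, add `subjid` to the CLASS statement and the same subject term to the ANOVA for consistency; its planned contrasts hardly change.

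The cost is one line of code and one table edit, with no new data. The slope CI becomes about 5-8% wider at correlations of 0.3 to 0.9.
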